Any patient (<18 years) who initiated first-line chemotherapy against primary ALL or AML at any of the four Danish departments of pediatric oncology from January 1st, 2008, to December 31st, 2022 (**Figure 1**). The eligible sample of children has been estimated to correspond to approximately 800 individuals who will be included in the cohort and subsequently be referred to as the intention-to-survey (ITS) population.

Data sources

Patients from the four Danish departments of pediatric oncology treating pediatric ALL and AML will be identified by searching the Danish Childhood Cancer Registry. The register holds data since 1985 on all children < 15 years with cancer and all children 15-17 years of age treated at a pediatric oncology department (13).

After cohort inclusion, data will be collected from the databases below, including the patient's medical records, hospital administrative databases, and national databases when applicable. The data for all cohort patients will be collected as listed in **Table 2**. For IMI patients only, additional data for a qualitative synthesis is collected, as detailed in **Table 3**.

- **The Danish Microbiology Database** is a nationwide database carrying all microbiology test results. We will search the database to identify factors that fulfill the criteria of direct or indirect proof of mold infection (Table 1).
- **The Danish Pathology Register is** a nationwide database carrying all pathology test results. We will search the database to identify histopathologic proof of mold infection.
- We will search the regional radiology databases for proof of mold infection, as this is not a nationwide database. We will explore the databases for radiologic interpretations of computed tomographies and magnetic resonance imaging to identify the IMI criteria (Table 1).
- Regional databases of blood test results will be searched to identify the neutrophilic count at the time of mold diagnosis in the IMI group and further to find proof of pancreatitis or hyperlipidemia.
- Patient records will be scrutinized to identify pre-leukemia comorbidities, leukemia diagnosis, and risk group, among other information, as listed in table 2 and table 3.

Data collection will start in April 2023.

Outcome variables

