The primary outcome is defined as IMI. To identify patients who develop IMI, all cohort patients will have their pathology, microbiology, and radiology records reviewed for documentation, qualifying for EORTC/MSG criteria for either proven or probable disease. As recommended for epidemiological studies, the possible disease category has been left out (3). In brief, IMI is classified as proven when there is tissue damage and histopathologic, cytopathologic, or microscopic documentation of infection; a fungal DNA amplification by polymerase chain reaction (PCR) in paraffin-embedded tissue; or culture samples from a normally sterile site suspicious of infection.

The probable IMI requires the presence of a host factor (hematologic malignancy, among others), clinical features, and mycological evidence. Clinical features comprise specific clinical, bronchoscopic, and/or radiologic findings showing signs of tracheobronchitis, pulmonary, sino-nasal, or central nervous system (CNS) infection. The mycological documentation is either direct, usual cultures from a non-sterile site (i.e., mold found in sputum) or indirect detection of Aspergillus galactomannan antigen. The criteria for "possible disease" are identical to "probable disease" but without the presence of mycological evidence (3) (see table 1). The outcome variable is binary (i.e., IMI yes or no), but an additional analysis will be made for the IMI subgroups (i.e., IMI proven or probable).

Exposure variables

The putative risk factors, referred to as 'exposures', are obtained from the patient's medical charts and corresponding paraclinical databases. These include antifungal medication, its type, dosing, and duration. It will be registered whether this was given as primary prophylaxis, treatment, or as secondary prophylaxis (after treated IMI). Also, preleukemic morbidities, treatment protocol, neutrophil granulocyte count at leukemia diagnosis, concomitant infections, and blood transfusion history, as a means of generalized toxicity, will be registered. Furthermore, therapy-related adverse effects, including gastrointestinal toxicity, neutropenic colitis, and treatment-related metabolic changes, including hyperglycosemia, pancreatitis, and hyperlipidemia (Table 2).

Observational period

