The period of IMI risk is defined as the period of active anticancer treatment. Exposure data from cohort subjects are collected from the date of cancer diagnosis until finished first-line chemotherapy, IMI occurrence, death, emigration, switching to a non-first-line treatment (e.g., treatment for induction failure or relapse), or 31st December 2022 (end of the study period), whichever comes first. For the IMI patients, we will also collect IMI outcome (cured, deceased, or emigrated) data after the IMI diagnosis for a narrative description of this group and to calculate the fatality rate.

Figure 1. STROBE flow diagram presenting the study design. ITS, intention to survey; ALL, acute lymphoblastic leukemia; AML, acute myelogenous leukemia (AML); IMI, invasive aspergillus.

Bias and limitations

As the cohort study is observational and retrospective, the study relies on data extracted from medical charts. To avoid imprecise documentation, the predominant amount of data is exact (i.e., blood values), whereas more loosely medical chart statements will be avoided as far as possible. There is no risk of 'recall bias,' as no patients or health care professionals will be contacted.

Another limitation in our study could be a small number of IMI patients and exposures; this would yield a low power and could be the reason for inconclusive findings. To avoid this and type 1 errors, we will report measures of association with confidence intervals; if these exclude measures of clinical interest, we will assume that our study is not limited by sample size and number of events (say, if the 95% confidence intervals around the Hazard Ratio reasonably precise [95%CI: 0.80 to 1.25]).

During the 15 years of study, the treatment protocols have changed. We will apply the analyses to the whole population and do subgroup analyses for patients according to their specific treatment protocols.

Statistical methods

The primary analyses will be based on the Intention to Survey (ITS) population, i.e., based on the Full Analysis Set (see Figure 1 illustrated above). To assess distributions and check for errors, variables will be summarized before analysis. The frequency of IMI in the cohort will be determined by calculating the cumulative incidence.

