Hazard ratios (HR) for ALL relative to AML will be estimated, with two-sided 95% confidence intervals, based on a Cox proportional-hazards model, with AL-type as the primary covariate. Equivalence will be shown if the limits of the two-sided 95% confidence interval exclude (less than) 0.80 and (more than) 1.25. Crude incidence rates will be expressed in patients with IMI events per 100 patient-years, with two-sided 95% confidence intervals. No multiplicity adjustments will be applied. P values, without adjustment for multiplicity, will be produced for all listed objectives. To identify independent risk factors for the development of IMI, regression models will be applied to explore which children were more likely to develop IMI (e.g., AL-type, sex, age at diagnosis, and related toxicities, see table 2).

All *P* values and 95% confidence intervals will be two sided. We will not apply explicit adjustments for multiplicity, rather we will analyze the secondary objectives in a prioritized order: The analyses of these will be performed in sequence until one of the analyses fails to show the statistically significant difference, or until all analyses have been completed at a statistical significance level of 0.05. The key secondary statistical tests will be reported with *P* values for hypothesis tests and claims of statistical significance.

Analyses will be performed using STATA software version 17 (StataCorp. 2021. Stata Statistical Software: Release 17. College Station, TX: StataCorp LLC.).

Patient and public involvement statement

As all data will be retrieved from patients no longer in active treatment, patients are not actively involved and were unfortunately not included in designing this study.

Ethics and dissemination

The relevant Danish authorities have approved the study, including the regional research legislation office "Regionssekretariat og jura, Syddanmark" (journal no. 22/7692), "Region Syddanmarks Interne Fortegnelse" (journal no. 22/15850), and by the involved departments. Other ethics approval has not been required for this study.

The study will be registered at Clinical.Trials.gov. The study acts under the Declaration of Helsinki. No patient will be contacted and is not exposed to any inconvenience. All data are confidential and will

be processed in accordance with the General Data Protection Regulation (GDPR) and The Danish Data Protection Act.

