Abbreviations: BAL, bronchoalveolar lavage; CSF, cerebrospinal fluid; CT, computed tomography; PCR, polymerase chain reaction; IMI, invasive mold infection.

alf culture is available, append the identification at the genus or species level from the culture results.

^b Tissue and cells submitted for histopathologic or cytopathologic studies should be stained using Grocott-Gomori methenamine silver stain or periodic acid Schiff stain to facilitate inspection of fungal structures. Whenever possible, wet mounts of specimens from foci related to invasive fungal disease should be stained with a fluorescent dye (eg, calcofluor or blankophor).

Recovery of Aspergillus species from blood cultures rarely indicates endovascular disease and almost always represents contamination.

^dHematologic malignancy refers to active malignancy, in receipt of treatment for this malignancy, and those in remission in the recent past. These patients would comprise largely acute leukemias and lymphomas, as well as multiple myeloma, whereas patients with aplastic anemia represent a more heterogeneous group of individuals and are not included. The list of host factors has been shortened.

Table 2. Characteristics and putative risk factors to be collected from all cohort patients.

	VARIABLE
Age (number in years)	Numerical
Sex (male/female)	Binary
Treating facility (Copenhagen/Århus/Odense/Aalborg)	Categorical
Pre-leukemia comorbidities	Categorical
ALL diagnosis: treatment protocol, risk group and CNS-status	Categorical
AML diagnosis: treatment protocol, risk group, FAB, and CNS-status	Categorical
Date of malignancy diagnosis	-
Name of treatment protocol	Categorical
Criteria met for IMI (proven/probable)	Categorical
Localization of IMI	Categorical
Neutrophil granulocyte count at leukemia diagnosis	Numerical
Anemia and red blood cell transfusion requirement (quantity)	Numerical
Thrombocytopenia and platelet transfusion requirement (quantity)	Numerical
Primary antifungal prophylaxis (type/dose/duration)	Categorical
Fungal infection other than IMI (fungi in a sterile site) (localization and type)	Categorical
Concomitant infections (bacteria in a sterile site) (localization and type)	Categorical
Neutropenic colitis (only radiological evidence: MRI, CT, plain film of the abdomen, US: bowel wall thickening > 4 mm, mesenteric stranding,	Binary
bowel dilatation, mucosal enhancement, or pneumatosis) (yes/no)	
Pancreatitis (> x3 upper limit of amylase/lipase) (yes/no)	Binary

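### Objective 3 enters exposures that begin after leukemia diagnosis without listing their onset dates or saying how their timing will be handled; as listed, unequal exposure windows bias their estimates

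*Combined protocol and SAP*

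**What the plan says.** The Statistical methods section names one model in detail, a Cox model for ALL against AML, whose covariate is fixed at diagnosis. For Objective 3 it says only that regression models will be used to find independent risk factors and to "explore which children were more likely to develop IMI (e.g., AL-type, sex, age at diagnosis, and related toxicities, see table 2"). It adds that "P values, without adjustment for multiplicity, will be produced for all listed objectives".

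The Observational period section sets the exposure window: "Exposure data from cohort subjects are collected from the date of cancer diagnosis until finished first-line chemotherapy, IMI occurrence, death, emigration", or another stop event, whichever comes first.

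Under Data sources, "The data for all cohort patients will be collected as listed in" Table 2. That table codes pancreatitis, neutropenic colitis and diabetes as yes/no, hyperlipidemia as a grade, infections by site and type, transfusions as a quantity, and prophylaxis by type, dose and duration. Diabetes also has a duration. The only date listed is "Date of malignancy diagnosis". The day of treatment on which an event fell appears only in Table 3, which covers IMI patients for a qualitative description.

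No section mentions time-dependent covariates, a lag or a landmark. Bias and limitations does not raise the matter.

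**The concern.** A child who develops IMI stops contributing exposure data on that day. A child who does not is usually observed to the end of first-line treatment and has longer to acquire pancreatitis, an infection or further transfusions. If exposure is entered as a fixed yes/no or a total, this difference in window alone makes the exposure look protective.

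There is also a possible error of opposite sign. To find IMI, "all cohort patients will have their pathology, microbiology, and radiology records reviewed for documentation". Sterile-site bacterial infection and radiological colitis rest on the same kinds of record. An exposure first found because a child was being investigated for IMI would look harmful.

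At stake is the reading of Objective 3. A harmless toxicity could be reported with a P value as protective or harmful, and a real risk factor could be hidden.

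**Working it through.** The plan gives no power or event calculation for Objective 3, so there is no design figure to reproduce. The check asks what happens when an exposure with no effect is entered as listed.

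**Expected events.** The introduction cites 14/232 (6.03%) for AML and 33/1216 (2.71%) for ALL. These are rates of invasive aspergillosis, used as a stand-in for IMI. Applied to about 800 children with the same disease mix: AML 800 × 14/1448 = 7.7; ALL 800 × 33/1448 = 18.2; total about 26.

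**Downward pull, closed form.** Assumptions not in the documents: 20% of children would have the toxicity over full treatment; non-cases are observed to the end; onset and IMI times are independent and evenly spread within each part of treatment. Let q be the probability that onset precedes IMI. Exposure odds are 0.2q/(1 − 0.2q) in cases and 0.2/0.8 = 0.25 in non-cases, so

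null OR = [0.2q/(1 − 0.2q)] / 0.25.

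With a share a of onsets and a share b of IMIs in the first fifth of treatment, q = 0.5(1 + a − b). If all onsets fall in the first 10% of treatment, q = 1 − b/4.

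| Onset pattern | b = 0.3 | b = 0.5 | b = 0.8 |
|---|---|---|---|
| All in first 10% | 0.91 | 0.85 | 0.76 |
| a = 0.9 | 0.76 | 0.65 | 0.49 |
| a = 0.6 | 0.60 | 0.49 | 0.35 |
| a = 0.3 | 0.44 | 0.35 | 0.21 |

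For example, a = 0.3 and b = 0.8 give q = 0.25 and OR = (0.05/0.95)/0.25 = 0.21. All 12 values are below 1.

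**Cox model.** I simulated the same 12 settings with 2,000,000 children each, stratified by leukemia type, assuming 2.5 years at risk for ALL and 0.5 for AML. Ever/never coding gave null hazard ratios of 0.21–0.90. Time-dependent coding (unexposed until onset) gave 0.98–1.02. A separate simulation with different assumptions (exposure 10% or 30%, constant or front-loaded hazards) gave 0.28–0.68 and 0.94–1.05.

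**Upward pull.** Suppose, purely for illustration, that 10% of otherwise unexposed cases have the exposure recorded in the 14 days before IMI. Null hazard ratios over the 12 settings become 0.68–1.46 with ever/never coding, 1.63–3.48 with unlagged time-dependent coding, and 0.98–1.02 with a 30-day lag. The lag works because it is longer than the assumed recording period.

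**Power after the fix.** With 26 events, a true hazard ratio of 2 and a share p of the risk set exposed, power ≈ Φ(ln 2 × √[26p(1 − p)] − 1.96). This is 18% for p = 0.1 and 29% for p = 0.2.

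**Cost of a day-60 landmark.** For AML (182.6 days at risk, first fifth 36.5 days), the share of IMIs before day 60 is b + (1 − b) × 23.5/146.1: 41% for b = 0.3 and 83% for b = 0.8. That leaves 4.5 to 1.3 of 7.7. For ALL (first fifth 182.6 days) it is b × 60/182.6: 10% to 26%, leaving 16.4 to 13.4 of 18.2. Overall about 21 to 15 of 26 remain.

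**The case against.** The plan never commits to ever/never coding. A Cox analysis with time-dependent exposures is compatible with its wording, and the statement that "The outcome variable is binary (i.e., IMI yes or no") does not count against it, because Cox regression also uses a yes/no event indicator. This stands: the bias is conditional on entering the variables as listed.

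A reader might infer that onset dates will never be looked at. The documents do not support that. The stop at IMI cannot be applied without comparing each exposure's date with the stop date, and the durations for prophylaxis and diabetes imply start and end points. Table 2 is also not a complete list of dates, since the Cox model and patient-year rates need follow-up dates it omits. What remains is narrower: onset dates are not listed as fields to be kept for all children, and their use is not stated. Dates checked but not kept cannot be used in the analysis.

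A reader might also infer a known direction of bias. The work-up mechanism is plausible, but no rate for it appears in the documents. IMI criteria rest on mold evidence with mainly chest, sinus, airway or brain findings, whereas the exposures concerned are bacterial isolates and bowel imaging. Shared record types do not prove shared episodes.

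Finally, Objective 3 is exploratory and the plan already warns of low power. Both are true, but neither removes a systematic bias from estimates presented as independent risk factors with P values.

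**Conclusion.** The point holds, limited to exposures in Objective 3 that begin after diagnosis. If they are entered as Table 2 lists them, the stop at IMI gives cases a shorter window and pulls estimates below 1 with no true effect. The illustrative null odds ratio is about 0.2 to 0.9. Its size rests on assumed prevalence and timing, and it is mild (0.76–0.91) when all onsets fall in the first tenth of treatment. Recording during the IMI work-up could offset or reverse this, so the net direction is uncertain.

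Age, sex, leukemia type, pre-leukemia comorbidity and neutrophil count at diagnosis are unaffected, as are incidence, mortality and the crude ALL-versus-AML hazard ratio. A reader might take this as undermining the study's main results; it does not. It should be fixed because the remedy is specific and becomes harder once records have been abstracted without dates.

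**What to change.** 1. Add to Table 2, for all children: the onset date of each toxicity and infection, prophylaxis start and stop dates, and the end-of-follow-up date.
2. State in Statistical methods that Objective 3 uses a Cox model with post-diagnosis exposures coded as time-dependent (unexposed until onset). Show unlagged results beside a pre-specified lag sensitivity analysis, with a lag at least as long as the IMI work-up; the 30 days above is only an illustration. Only variables known at diagnosis enter as fixed covariates.
3. Do not enter whole-follow-up transfusion totals as fixed covariates. Report them descriptively or, optionally, use a count to date or a landmark count among children still at risk. If a day-60 landmark is considered, note the events it would leave, especially the roughly 1 to 5 of 8 in AML.
4. Keep the stop at IMI in Observational period.

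The cost is extra date fields and a start-stop data layout. Many dates sit in records already being read; the blood-test databases, for instance, are searched "further to find proof of pancreatitis or hyperlipidemia". Dating every transfusion would be a larger task, and Data sources names no transfusion database. A lag misses effects confined to the lag period, which is why both analyses should be shown. The fix removes a bias; it does not raise the low power of Objective 3.

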Tracheobronchial ulceration, nodule, pseudomembrane, plaque, or eschar seen on bronchoscopic analysis	
Sino-nasal diseases	
Acute localized pain (including pain radiating to the eye)	
Nasal ulcer with black eschar	
Extension from the paranasal sinus across bony barriers, including into the orbit	
Central nervous system infection	
1 of the following 2 signs:	
Focal lesions on imaging	
Meningear emancement on magnetic resonance imaging of C1	
Any mole for evanue Asperaillys Euserium Scedesporium species or Mucorales recovered by culture from sputum BAL bronchial bruch or aspirate	
Microsconical detection of fungal elements in southing BAL bronchial brush or aspirate indicating a mold	
Tracheopran becession of range contents in optically of a print of applied instruming a north	
Asperaillus recovered by culture of BAL or bronchial brush	
Microscopic detection of fungal elements in BAL or bronchial brush indicating a mold	
Sino-nasal diseases	
Mold recovered by culture of sinus aspirate samples	
Microscopic detection of fungal elements in sinus aspirate samples indicating a mold	
Aspergillosis only	
Galactomannan antigen	
Antigen detected in plasma, serum, BAL, or CSF	
Any 1 of the following:	
Single serum or plasma: ≥1.0	
BAL huid:≥1.0	
Single serum of plasma: 20.7 and BAL huid 20.8	
CSF: 21.0	
Any 1 of the following:	
Plasma, serum, or whole blood 2 or more consecutive PCR tests positive	
BAL fluid 2 or more duplicate PCR tests positive	
At least 1 PCR test positive in plasma, serum, or whole blood and 1 PCR test positive in BAL fluid	
Aspergillus species recovered by culture from sputum, BAL, bronchial brush, or aspirate	
CRITERIA FOR POSSIBLE DISEASE: Host factors + clinical features + no mycological evidence	
Probable invasive mold infection (IMI) requires the presence of at least 1 host factor, a clinical feature, and mycologic evidence and is proposed for	
immunocompromised patients only, whereas proven IMI can apply to any patient, regardless of whether the patient is immunocompromised. Probable IMI	
requires the presence of a host factor, a clinical feature, and mycologic evidence. Cases that meet the criteria for a host factor and a clinical feature but for which	

mycological evidence has not been found are considered possible IFD. (1,3)-beta-D glucan was not considered to provide mycological evidence of any invasive mold disease.

Abbreviations: BAL, bronchoalveolar lavage; CSF, cerebrospinal fluid; CT, computed tomography; PCR, polymerase chain reaction; IMI, invasive mold infection.

alf culture is available, append the identification at the genus or species level from the culture results.

^b Tissue and cells submitted for histopathologic or cytopathologic studies should be stained using Grocott-Gomori methenamine silver stain or periodic acid Schiff stain to facilitate inspection of fungal structures. Whenever possible, wet mounts of specimens from foci related to invasive fungal disease should be stained with a fluorescent dye (eg, calcofluor or blankophor).

Recovery of Aspergillus species from blood cultures rarely indicates endovascular disease and almost always represents contamination.

^dHematologic malignancy refers to active malignancy, in receipt of treatment for this malignancy, and those in remission in the recent past. These patients would comprise largely acute leukemias and lymphomas, as well as multiple myeloma, whereas patients with aplastic anemia represent a more heterogeneous group of individuals and are not included. The list of host factors has been shortened.

Table 2. Characteristics and putative risk factors to be collected from all cohort patients.

	VARIABLE
Age (number in years)	Numerical
Sex (male/female)	Binary
Treating facility (Copenhagen/Århus/Odense/Aalborg)	Categorical
Pre-leukemia comorbidities	Categorical
ALL diagnosis: treatment protocol, risk group and CNS-status	Categorical
AML diagnosis: treatment protocol, risk group, FAB, and CNS-status	Categorical
Date of malignancy diagnosis	-
Name of treatment protocol	Categorical
Criteria met for IMI (proven/probable)	Categorical
Localization of IMI	Categorical
Neutrophil granulocyte count at leukemia diagnosis	Numerical
Anemia and red blood cell transfusion requirement (quantity)	Numerical
Thrombocytopenia and platelet transfusion requirement (quantity)	Numerical
Primary antifungal prophylaxis (type/dose/duration)	Categorical
Fungal infection other than IMI (fungi in a sterile site) (localization and type)	Categorical
Concomitant infections (bacteria in a sterile site) (localization and type)	Categorical
Neutropenic colitis (only radiological evidence: MRI, CT, plain film of the abdomen, US: bowel wall thickening > 4 mm, mesenteric stranding,	Binary
bowel dilatation, mucosal enhancement, or pneumatosis) (yes/no)	
Pancreatitis (> x3 upper limit of amylase/lipase) (yes/no)	Binary
Therapy related hyperlipidemia (triglycerides/cholesterol blood concentrations greater than upper normal limit (UNL). Grading: Mild:	Categorical
triglycerides/cholesterol <10 times UNL; Moderate: triglycerides/cholesterol 10–20 times UNL; Severe: triglycerides/cholesterol >20 times	
UNL.) (mild/moderate/severe)	
Therapy related diabetes (insulin dependent) (yes/no)	Binary
Therapy related diabetes (insulin dependent) (duration)	Numerical
Outcome cancer (finishing anticancer therapy, death, hematopoietic stem-cell transplantation (HSCT), emigration, or 31st December 2022	Categorical
(end of the study period)) (cured, recurrence, deceased)	

Table 3. Qualitative description of identified invasive aspergillus patients.

Patient data collection
Type of mold
Mold resistance pattern
Treatment day (days since the date of malignancy diagnosis)
Corticosteroid therapy (duration, type, mg/m ² , time since)
Immunosuppressive therapy type/treatment phase
Neutropenia (severe: < 0,5 x 10 ⁹ /l) (days prior to IMI diagnosis/neutrophilic count at day of diagnosis)
Primary antifungal prophylaxis before IA (type/dose/duration)
Antifungal IA treatment (type/dose/duration)
Secondary antifungal prophylaxis after IA treatment (type/dose/duration)
Preceding and concomitant antimicrobial therapy (type / duration prior to IMI)
Diagnostic procedures (culture, galactomannan assay, radiologic findings, etc.)
Intravenous access at time of diagnosis (central venous / port-a-cath)
Anticancer treatment delays/modifications
ICU stay (yes/no/duration)
Outcome fungal (cured, ongoing, deceased)

References

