Few studies have examined the incidence according to the currently used "European Organization for Research and Treatment of Cancer/Invasive Fungal Infections Cooperative Group and the National Institute of Allergy and Infectious Diseases Mycoses Study Group" (EORTC/MSG) guidelines for a proven, probable, or possible IMI (3). An Australian 10-year epidemiological study, however, indicates an incidence of invasive aspergillosis in patients treated for acute myelogenous leukemia (AML) and acute lymphoblastic leukemia (ALL) of (14/232) 6%, (33/1216) 2.7 %, respectively (4, 5). Only few epidemiologic reports have been performed in Denmark or Scandinavia (6).

Despite progress in the diagnosis, prevention, and management of IMI, the reported mortality rates are often high. In an epidemiologic multicenter study, the main proportion of molds was A. fumigatus, with a mortality rate of 30% (7). A number of risk factors have been associated with IMI, among these, corticosteroid exposure, neutropenia, as well as different chemotherapy and conditioning regimens. However, few studies have addressed this in children with cancer, and knowledge regarding individual risk prediction for developing IMI in immunosuppressed children remains sparse (8, 9). Besides established risk factors for IMI, other treatment-related toxicities, including metabolic changes and gastrointestinal toxicity, may also be related to infectious morbidity (10-12).

Our aim is to obtain an epidemiological overview of IMI in children receiving first-line treatment for ALL or AML in Denmark and identify possible risk factors, including treatment-related adverse effects.

Objectives

1. To determine and compare the incidence of IMI in childhood AML and ALL during first-line chemotherapy in Denmark.

2. To determine and compare the mortality of IMI in childhood AML and ALL during first-line chemotherapy in Denmark.

3. To explore risk factors for IMI in childhood AML and ALL during first-line chemotherapy in Denmark.

METHODS

Study design

A retrospective nationwide multicenter, open cohort study of all children who received first-line chemotherapy against acute leukemia from January 1st, 2008, to December 31st, 2022, in a Danish pediatric oncology unit; this includes data from the four Danish tertiary pediatric oncology units at Rigshospitalet, Aarhus University Hospital, Odense University Hospital, and Aalborg University Hospital.

Study population

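### Table 2 does not separate tested-and-normal from never-tested for pancreatitis, neutropenic colitis and hyperlipidemia, so objective 3 cannot tell a toxicity association from differential investigation

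*Combined protocol and SAP*

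**What the plan says.** The design is "A retrospective nationwide multicenter, open cohort study of all children who received first-line chemotherapy against acute leukemia" (Study design). Exposures "are obtained from the patient's medical charts and corresponding paraclinical databases" (Exposure variables). Regional blood-test databases are searched for the neutrophil count in IMI patients and "further to find proof of pancreatitis or hyperlipidemia" (Data sources).

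Table 2 then sets the response levels:

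- Pancreatitis: "Pancreatitis (> x3 upper limit of amylase/lipase) (yes/no", typed binary.
- Neutropenic colitis: "Neutropenic colitis (only radiological evidence: MRI, CT, plain film of the abdomen, US: bowel wall thickening > 4 mm, mesenteric stranding" and further imaging signs, typed binary.
- Hyperlipidemia: graded by multiples of the upper normal limit, ending "UNL.) (mild/moderate/severe". Neither a normal nor an unmeasured level is listed.

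The outcome is also found from existing investigations: "all cohort patients will have their pathology, microbiology, and radiology records reviewed for documentation" (Outcome variables). Statistical methods puts the Table 2 toxicities into regression models as possible independent risk factors for IMI. Observational period ends exposure collection at IMI or at the other stopping events.

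**The concern.** Pancreatitis is visible only if amylase or lipase was measured, hyperlipidemia only if lipids were measured, and neutropenic colitis only if the abdomen was imaged. Nobody scheduled those tests for the study. A database search for proof returns positive findings, and the levels in Table 2 leave no place to record that a child was never examined.

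If testing differs between children who go on to IMI and those who do not, recorded toxicity will differ even where true toxicity does not. Heavier monitoring of sicker children, or a work-up in the days before an IMI diagnosis, could produce such a difference, and more investigation may also raise detection of IMI itself. Testing habits may vary across four centres and 15 years of changing protocols.

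Bias and limitations does not cover this. It prefers exact blood values to loose chart statements, which protects accuracy among tested children but says nothing about who was tested. At stake is the reading of objective 3. Anonymized raw data are also to be published, and later users could not recover the distinction if it was never recorded.

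**Working it through.** **Which variables are affected.** Pancreatitis and neutropenic colitis are yes/no and wholly defined by a test or scan. Hyperlipidemia is graded, with the same gap. "Therapy related diabetes (insulin dependent) (yes/no" rests on insulin dependence rather than a laboratory threshold, so it is less exposed.

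**Figures in the plan.** None bears on this point, so there is nothing to reproduce. The documents give no testing rates or toxicity prevalences. Everything below is illustrative.

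**Step 1: what drives the bias when all children are analysed.** Assume true prevalence p is the same in IMI and non-IMI children (true odds ratio 1), the test is perfect, and untested children count as unaffected. Let s1 and s0 be the share tested *among affected children* in the IMI and non-IMI groups. Recorded prevalence is p·s1 and p·s0, so

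OR = [p·s1/(1 − p·s1)] / [p·s0/(1 − p·s0)].

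With p = 0.10:

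| s1 | s0 | Calculation | OR |
|---|---|---|---|
| 80% | 40% | (0.08/0.92)/(0.04/0.96) | 2.09 |
| 60% | 40% | (0.06/0.94)/(0.04/0.96) | 1.53 |
| 95% | 80% | (0.095/0.905)/(0.08/0.92) | 1.21 |
| 95% | 90% | (0.095/0.905)/(0.09/0.91) | 1.06 |
| 95% | 95% | equal | 1.00 |
| 40% | 80% | (0.04/0.96)/(0.08/0.92) | 0.48 |

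Prevalence matters little: at p = 0.05 the first row gives 2.04.

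**Step 2: overall testing is not the relevant quantity.** Let 95% of affected children be tested in both groups, and 80% (IMI) versus 40% (non-IMI) of unaffected children. Overall testing is 0.095 + 0.90 × 0.80 = 81.5% versus 0.095 + 0.90 × 0.40 = 45.5%. Recorded prevalence is 9.5% in both, so OR = 1.00 despite very unequal testing.

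**Step 3: restricting to tested children is no cure.** In the Step 2 setting the tested-only odds ratio is (0.095/0.72)/(0.095/0.36) = 0.50, a false protective effect. If testing is instead unrelated to true toxicity status, tested-only returns 1.00. Making not tested its own level and comparing present with tested-and-absent is, unadjusted, the same contrast with the same weakness.

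**Step 4: a shared-cause version.** Assume 30% of children are intensively investigated, true IMI risk is 3%, and toxicity (10%) and IMI are independent. If toxicity testing is 90% versus 30% and IMI detection 90% versus 40% in the intensive and other children:

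- recorded toxicity: 0.10 × (0.3 × 0.9 + 0.7 × 0.3) = 0.048
- detected IMI: 0.03 × (0.3 × 0.9 + 0.7 × 0.4) = 0.0165
- both: 0.003 × (0.3 × 0.81 + 0.7 × 0.12) = 0.000981
- RR = (0.000981/0.048) / [(0.0165 − 0.000981)/0.952] = 1.25

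With 90% versus 40% and 90% versus 60% the RR is 1.09. If IMI detection does not depend on intensity, it is 1.00.

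**The case against.** A reader might infer that the coding will inflate toxicity associations, perhaps to twofold. The documents do not support that. The 2.09 needs a large difference in testing among affected children. If symptoms lead nearly all of them to be tested, the bias is close to nil. The direction could also reverse: exposure collection stops at IMI while other children are followed longer, so IMI cases may have less time in which to be tested. The same cut-off removes tests done after IMI. All of this stands. The cut-off does not remove a work-up shortly before diagnosis or heavier monitoring of sicker children.

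It is also tempting to say that untested children will be coded as unaffected. Table 2 lists variables and types, not a coding rule, and a blank entry would be compatible with it. What can be said is that no level makes the distinction and no text says how it will be handled.

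Objective 3 is exploratory and the exposures are called putative. Subgroup analyses by treatment protocol are planned, and treating facility is recorded. These could absorb some differences in monitoring, but not differences between children within a protocol or centre.

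**Conclusion.** The point holds as a gap in data capture, not as a demonstrated bias. For three Table 2 exposures, the plan cannot show whether investigation was even, and so cannot separate a toxicity association from differential investigation. The illustrative odds ratio runs from about 0.5 to 2 with 40% and 80% testing among affected children in either arrangement, and is 1.0 if testing among them is equal. These rates are assumptions; the true size and direction are unknown.

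The concern is strongest for hyperlipidemia if, as assumed here, it is often found only because lipids were measured. It is weaker for pancreatitis and neutropenic colitis if symptoms usually prompt the test, also an assumption. Ending collection at IMI reduces the problem without removing it. Only objective 3 is affected; the incidence and mortality objectives do not depend on these variables. The change should be made, but the study does not stand or fall on it.

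**What to change.** 1. In Table 2, code pancreatitis and neutropenic colitis as present / tested and absent / not tested, and hyperlipidemia as normal / mild / moderate / severe / not tested. Count only tests before IMI or the end of follow-up, drawn from the databases already searched.
2. Report the proportion tested for each variable by IMI status, leukemia type, treatment protocol and centre.
3. Keep the analysis of all children as the main one, and state how untested children enter it.
4. Add one sensitivity analysis that either treats not tested as its own level or is restricted to tested children. State that the tested set is itself selected and can be biased in either direction.
5. Do not make agreement between the two analyses a condition for naming a risk factor. Where testing differs materially, report the association as possibly due to detection.

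The cost is modest extra extraction for about 800 children, partly from regional systems, and one further analysis with fewer children. Precision will be limited: applying the cited aspergillosis incidences to the whole cohort gives roughly 800 × 33/1216 = 22 to 800 × 14/232 = 48 cases. If testing proves near-uniform, the table of proportions tested will show it and strengthen the result.
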